#### 8.1.1 Serious adverse event definitions

Serious adverse events (SAEs) are defined in the CLEE011A2404 protocol. Those serious adverse events considered by the investigator to be possibly related to a biomarker collection procedure performed as part of this protocol will be indicated as such in the AE eCRF in the CLEE011A2404 EDC system.

#### 8.1.2 Serious adverse event reporting

SAEs will be collected and reported as described in the CLEE011A2404 protocol. If the event is suspected to be causally related to a biomarker collection procedure, as assessed by the investigator, it will be identified as such. SAEs will be followed until resolution or until clinically relevant improvement or stabilization. SAE collection ends 14 days after the last biomarker collection procedure.

Any SAEs experienced after this 14 day period should only be reported to Novartis if the investigator suspects a causal relationship to a biomarker collection procedure performed as part of this companion sample collection protocol. Recurrent episodes, complications, or progression of the initial SAE must be reported as follow-up to the original episode within 24 hours of the investigator receiving the follow-up information. An SAE occurring at a different time interval or otherwise considered completely unrelated to a previously reported one should be reported separately as a new event.

Information about all SAEs is collected and recorded on the Serious Adverse Event Report Form; all applicable sections of the form must be completed in order to provide a clinically thorough report. The investigator must assess and record the relationship of each SAE to the biomarker collection procedures, complete the SAE Report Form in English, and send the completed, signed form by fax within 24 hours to the oncology Novartis Drug Safety and Epidemiology (DS&E) department.

The telephone and telefax number of the contact persons in the local department of Drug Safety and Epidemiology (DS&E), specific to the site, are listed in the investigator folder provided to each site. The original copy of the SAE Report Form and the fax confirmation sheet must be kept with the case report form documentation at the study site.

Follow-up information is sent to the same contact(s) to which the original SAE Report Form was sent, using a new SAE Report Form stating that this is a follow-up to the previously reported SAE and giving the date of the original report. Each re-occurrence, complication, or progression of the original event should be reported as a follow-up to that event regardless of when it occurs. The follow-up information should describe whether the event has resolved or continues, if and how it was treated, and whether the patient continued or withdrew from study participation.

If the SAE is thought to be related to a biomarker collection procedure performed as part of the CLEE011AUS42 protocol, an oncology Novartis Drug Safety and Epidemiology (DS&E) department associate may urgently require further information from the investigator for Health Authority reporting. Novartis may need to issue an Investigator Notification (IN), to inform all investigators involved in the CLEE011AUS42 study that this SAE has been reported. Suspected Unexpected Serious Adverse Reactions (SUSARs) will be collected and reported to the competent authorities and relevant ethics committees in accordance with Directive 2001/20/EC or as per national regulatory requirements in participating countries.

## **9 Data collection and management**

### **9.1 Data confidentiality**

Information about study subjects will be kept confidential and managed under the applicable laws and regulations. Those regulations require a signed subject authorization informing the subject of the following:

- What protected health information (PHI) will be collected from subjects in this study
- Who will have access to that information and why
- Who will use or disclose that information
- The rights of a research subject to revoke their authorization for use of their PHI.

In the event that a subject revokes authorization to collect or use PHI, the investigator, by regulation, retains the ability to use all information collected prior to the revocation of subject authorization. For subjects that have revoked authorization to collect or use PHI, attempts should be made to obtain permission to collect follow-up safety information (e.g. has the subject experienced any new or worsened AEs) at the end of their scheduled study period.

The data collection system for this study uses built-in security features to encrypt all data for transmission in both directions, preventing unauthorized access to confidential participant information. Access to the system will be controlled by a sequence of individually assigned user identification codes and passwords, made available only to authorized personnel who have completed prerequisite training. Data from this study will be combined with data from other studies, including but not limited to the treatment study CLEE011A2404 on which the patient received the investigational agent(s).

## **9.2 Site monitoring**

Before study initiation, at a site initiation visit or at an investigator's meeting, Novartis personnel (or designated CRO) will review the protocol and central laboratory requisition forms with the investigators and their staff. During the study, the field monitor will visit the site regularly to check the completeness of patient records, the accuracy of entries on the requisition forms, the adherence to the protocol to Good Clinical Practice and the progress of enrollment. Key study personnel must be available to assist the field monitor during these visits.

The investigator must maintain source documents for each patient in the study, consisting of case and visit notes (hospital or clinic medical records) containing demographic and medical information, laboratory data, and the results of any other tests or assessments. All information recorded on the requisition forms must be traceable to source documents in the patient's file. The investigator must also keep the original signed informed consent form (a signed copy is given to the patient).

The investigator must give the monitor access to all relevant source documents to confirm their consistency with the completed central laboratory requisition forms. Novartis monitoring standards require full verification for the presence of informed consent, adherence to the inclusion/exclusion criteria and documentation of SAEs. Additional checks of the consistency of the source data with the requisition forms are performed according to the study-specific monitoring plan.

## **9.3 Data collection**

Biomarker (blood and tissue) samples drawn during the course of this companion sample collection protocol will be collected from the Investigator sites and analyzed by a Novartis assigned laboratory or contracted central lab. The results will be sent electronically to Novartis. Designated investigational site staff will complete the information required by the protocol into the appropriate central laboratory requisition forms (printed on 2 or 3-part non-carbon-required paper). Field monitors will review the central laboratory requisition forms for accuracy and completeness and instruct site personnel to make any required corrections or additions. One copy of the requisition form will be forwarded to each analytical laboratory

with the respective samples by the designated investigational site staff, and one copy will be retained at the investigational site.

The Principal Investigator is responsible for assuring that the data entered on the central laboratory requisition forms is complete, accurate, and that entry and updates are performed in a timely manner.

## **10 Statistical methods and data analysis**

This companion sample collection protocol seeks to explore the mechanisms of resistance to cancer treatment through the analysis of data from tumor samples at baseline and after development of disease progression, [REDACTED]

[REDACTED] Analyses are considered exploratory in nature and the detailed data analysis plan(s) will be described in stand-alone documents or, where appropriate, in the individual Statistical Analysis Plan (SAP) from corresponding parent treatment studies for inclusion in the respective CSRs.

Broadly, data analyses will seek to (1). analyze mutations present at the initial diagnosis of HR+/HER2- advanced breast cancer across diverse ethnicities (2). characterize the mutations identified at progression of disease following the treatment of ribociclib + letrozole and (3). characterize the immune response to ribociclib + letrozole. Descriptive statistics and exploratory modeling will be used. Details will be described in the data analysis plans.

### **10.1 Analysis sets**

The biomarker analysis set (BAS) includes all US subjects with evaluable biomarker assessment from the Full Analysis set of CLEE011A2404 study.

### **10.2 Patient demographics/other baseline characteristics**

Demographic and other baseline data including disease characteristics and prior treatment will be listed and summarized descriptively for the BAS.

Categorical data will be presented as frequencies and percentages. For continuous data, mean, standard deviation, median, minimum, and maximum will be presented.

Relevant medical histories and current medical at baseline will be summarized by system organ class and preferred term.

### **10.3 Statistical analysis plan**

Details of the analyses including primary analysis to be performed will be described in a corresponding statistical analysis plan.

### **10.4 Safety reporting**

#### **10.4.1 Serious adverse events (AEs)**

Summary tables for serious adverse events (AEs) have to include only AEs that are only suspected to be related to the biomarker collection procedures in the opinion of the investigator. Biomarker collection-related SAEs will be summarized by system organ class

[REDACTED]

and/or preferred term, severity (based on CTCAE grades) and type of serious adverse event. These will be reported in the CLEE011A2404 EDC system with a comment that the SAE is related to the companion sample collection protocol CLEE011AUS42 protocol.

Deaths reportable as SAEs and non-fatal serious adverse events will be listed by patient and tabulated by type of adverse event and treatment group.

Review of these safety data will be conducted on an on-going basis by members of the study team. The findings will be documented and will be made available upon request.

## **10.5 Sample size calculation**

Not applicable. All US subjects from CLEE011A2404 will be included in this study.

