## Synopsis

Title	A companion sample collection protocol to support the discovery of breast cancer aberrations with treatment of/LEE011/Ribociclib
Sponsor and Clinical	Novartis – Region US
Phase	I/II
Investigation/Study Type	Interventional
Purpose and Rationale	
The purpose of this US only companion sample collection protocol of the Global Phase IIIb trial (CLEE011A2404) is to (1). investigate the aberrations of common pathways for HR+ breast cancer at baseline in all consented patients enrolled in this companion sample collection protocol (2). evaluate genetic mutations in tumor following the progression on ribociclib (3). assess various mutations in diverse patient populations at diagnosis (4).
 
Primary Objective(s)	Determine the various modes of resistance to ribociclib following progression of disease.
Secondary Objectives	
Secondary:
 

- To assess the mutational aberrations across a diverse patient population with newly diagnosed HR+ HER2- advanced breast cancer.

 
Study Design and Assessments	
This is a multicenter, US specific, non-treatment based companion sample collection protocol. This protocol will evaluate the aberrations of common pathways for newly diagnosed HR+/HER2- advanced breast cancer tumors and responses to ribociclib in diverse patient populations. This companion sample collection protocol is available for all US patients enrolled on CLEE011A2404 (CompLEEment-1) and will not alter the planned treatment. Tumor collection required for this study will occur at two time points: at baseline/screening and upon the development of progressive disease as shown in Section 7.2.
 
The analyses of samples will be conducted in an on-going fashion as tumor tissue from patients becomes available. Sites will be provided with the results the genetic mutation profiles of their patients' tumor upon progression.

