## 2.2 Rationale for study design

Tumor tissue samples will be collected in this trial at baseline to identify biomarkers that may be predictive of benefit from the combination of ribociclib and letrozole, understand the mutations present in newly diagnosed advanced breast cancer patients and to understand the heterogeneity of mutations across diverse patient populations. Tumor samples will also be collected at time of progression (End of Treatment). This will be done using both Nanostring and multiplexed approaches (Next Gen Sequencing) of but not limited to CCND1, CDKN2A, PIK3CA and PTEN as well as protein expression profiling of PDL-1 and CD8 using AQUA (Automated Quantitative Analysis), a fluorescent IHC. The biopsy collected at progression/end of treatment will be dedicated to understanding resistance to treatment of ribociclib in combination with letrozole as well as immune profiling of this patient population. This study also provides a unique opportunity to investigate the various mutations in a heterogeneous patient population with HR+/HER2- advanced breast cancer at initial diagnosis and following progression to CDK4/6 inhibition.

[figure not shown]
Tumor samples will be requested at baseline and following progression. Tumor tissue samples will be obtained only from patients who consent to participating in this sample tumor collection and will be sent to a third party central laboratory for analysis. All sites that participate in this study will receive the results of the genetic mutation of their patients' tumor tissue profile upon progression.

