### **3 Objectives and endpoints**

This is a non-interventional study to allow for the collection of tumor and normal tissue samples [REDACTED] to better understand relevant mutations and the mechanisms responsible for resistance to treatment.

	Objective	Endpoint
Primary	Determine the various modes of resistance to ribociclib following progression of disease	Mutations of genes that are relevant to HR+ and the CDK4/6 pathway such as but not limited to CCND1, CDKN2A, PIK3CA and PTEN to identify the potential mechanisms of progression.
Secondary	To assess the mutational aberrations across a diverse patient population with newly diagnosed HR+ HER2- advanced breast cancer	Differences in mutations will be assessed based on baseline samples and compared across diverse races/ethnicities with HR+ HER2- advanced breast cancer - specifically Caucasian, African America, Hispanic, Native American and Pacific Islander.

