## 5.2 Exclusion criteria

Patients eligible for this companion sample collection protocol must not meet **any** of the exclusion criteria in the CLEE011A2404 study, in addition to the following:

1. Patients without either fresh or archival tumor tissue accessible.

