#### 7.1.1.1 Screen failures

Patients who sign an ICF but fail to undergo a biopsy (or provide archival tissue) or are otherwise found to be ineligible after signing the study ICF will be considered screen failures for this protocol. Patients identified as screen failures under the treatment protocol CLEE011A2404 will not be enrolled under this protocol.

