#### **7.1.3.2 Premature withdrawal**

Patients may voluntarily withdraw from either the CLEE011A2404 and/or this study CLEE011AUS42 or be dropped from it at the discretion of the investigator at any time. The reason for discontinuation will be recorded on the applicable corresponding eCRFs in the CLEE011A2404 EDC database (if patient is withdrawn from the CLEE011A2404 study) and captured on the central laboratory requisition form for US companion sample collection protocol CLEE011AUS42.

If a patient withdraws consent, Novartis will continue to retain and use all research results that have already been collected for the study evaluation. All biological samples that have already been collected may be retained and analyzed at a later date.

If a patient withdraws from the CLEE011A2404 study, the investigator will still receive the output of the data collected from this study up to the time point of the patient's withdrawal.

If a patient withdraws consent, the investigator must make every effort (e.g. telephone, e-mail, letter) to determine the primary reason for this decision and record this information. Study treatment must be discontinued and no further assessments conducted.

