## **11.3 Informed consent procedures**

Eligible patients may only be included in the study after providing written, IRB/IEC/REB-approved informed consent.

Informed consent must be obtained before conducting any study-specific procedures (i.e. all of the procedures described in the protocol). The process of obtaining informed consent should be documented in the patient source documents. The date when a subject's Informed Consent was actually obtained will be captured in the appropriate central laboratory requisition forms.

Novartis will provide to investigators, in a separate document, a proposed Informed Consent Form (ICF) that is considered appropriate for this study and complies with the ICH GCP guidelines and regulatory requirements. Any changes to this ICF suggested by the investigator must be agreed to by Novartis before submission to the IRB/IEC/REB and a

copy of the approved version must be provided to the Novartis monitor after IRB/IEC/REB approval.

This protocol includes only men and post-menopausal women. However, all participants should be informed that taking the study medication may involve unknown risks to a fetus if pregnancy were to occur during the study and agree that in order to participate in the study they must adhere to the contraception requirement for the duration of the study. If there is any question that the patient will not reliably comply, they should not be entered in the study.

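### Does Section 10.5's claim that all US subjects of CLEE011A2404 are included need correcting, when the entry rules admit only those who consent and provide tissue?

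*Combined protocol and SAP*

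**What the plan says.** Section 10.5 is the only statement on sample size: "Not applicable. All US subjects from CLEE011A2404 will be included in this study".

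Other sections make inclusion conditional:

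- **Consent.** Section 11.3: "Eligible patients may only be included in the study after providing written, IRB/IEC/REB-approved informed consent". Section 2.2 says the same of the samples: "Tumor tissue samples will be obtained only from patients who consent to participating in this sample tumor collection". Section 7.1.1 shows that the companion protocol has its own consent form.
- **Accessible tissue.** Section 5.2 adds one exclusion to those of the parent trial: "Patients without either fresh or archival tumor tissue accessible".
- **Tissue provided.** Section 7.1.1.1 covers "Patients who sign an ICF but fail to undergo a biopsy (or provide archival tissue") and classes them as screen failures for this protocol.
- **Withdrawal.** Section 7.1.3.2: "Patients may voluntarily withdraw from either the CLEE011A2404 and/or this study CLEE011AUS42".

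The Synopsis describes the baseline population as "all consented patients enrolled in this companion sample collection protocol", which agrees with the consent rule and not with Section 10.5. Section 4.1 says only that the protocol is open to all US patients of the parent trial.

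Section 10.1 defines one analysis set, the biomarker analysis set: US subjects in the parent trial's Full Analysis Set who have an evaluable biomarker assessment. Sections 10 and 10.3 call the analyses exploratory and leave their detail to separate analysis plans.

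**The concern.** Section 10.5 appears to offer complete coverage of the US subjects as the reason no sample size is needed. If coverage is not complete, that reason fails and the plan is left without an expected number of patients for any objective.

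This would matter most for the primary objective, "Determine the various modes of resistance to ribociclib following progression of disease". It can be informed only by participants who progress, are biopsied again before their next therapy, and yield an evaluable result. The secondary comparison across race and ethnicity groups uses baseline tissue and, under Section 7.2.3, only what remains in adequate quantity and quality. The immune profile in Section 4.1 needs tissue from before and after treatment. These are three different denominators, while the single analysis set names no time point. A reader who took Section 10.5 at its word might think the progression findings describe nearly all US subjects when they describe a self-selected part of them.

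The timing of archival samples also seems inconsistent. Footnote 2 of Table 7-1 allows them in the first month of treatment, whereas Table 7-2 lets them arrive whenever storage releases them. If a late sample turned its donor into a screen failure, the two tables could give different baseline populations.

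**Working it through.** The plan gives no figure to reproduce: no N, alpha, power, effect size, consent rate or attrition rate. The check is therefore textual.

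**1. Is the sentence literally true?** Only if every US subject consents, has accessible tissue and provides it. The protocol provides for failure of each condition (Sections 11.3, 5.2 and 7.1.1.1), so as written the sentence is too broad. The withdrawal rule adds nothing here. It governs leaving, not entry, and Section 7.1.3.2 keeps results already collected and allows samples already taken to be analysed later.

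**2. Does anything depend on the sentence?**

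| Function | Governing section | Uses Section 10.5? |
|---|---|---|
| Who may enter | 5.1, 5.2, 7.1.1, 11.3 | No |
| Who is a screen failure | 7.1.1.1 | No |
| Who is analysed | 10.1 | No |
| Population for baseline summaries | 10.2 (the biomarker analysis set) | No |
| Type of analysis | 10 (exploratory, descriptive) | No |

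A patient who declines consent, or gives no tissue, has no evaluable assessment under this protocol and so drops out of the Section 10.1 set, whatever Section 10.5 says.

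**3. Are the denominators open?** Section 3 ties the secondary endpoint to baseline samples. Sections 3 and 10 tie the primary objective to progression. Section 4.1 ties the immune profile to both. An analyst would take the subjects evaluable at the time point each objective needs. The remaining detail is assigned to the separate plan under Section 10.3, which is not among the documents reviewed.

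**4. Does archival timing change who is analysed?** The Synopsis and Section 4.1 allow an archival sample to be sent after treatment starts, which is compatible with a first-month window. The real difference is footnote 2 of Table 7-1 against one cell of Table 7-2. Section 7.1.1.1 concerns tissue that is never provided and sets no deadline. Section 10.1 sets no shipment date. Section 12 bars requests to approve deviations, but it also says significant deviations are recorded and reported; it does not remove a sample. No effect on the analysed set is shown.

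**5. What numbers could be at stake?** All rates here are assumptions; none is in the documents. Let N be US enrolment, f the share who consent and give baseline tissue, and g the share of those with an evaluable progression sample. Then n = N × f × g.

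- With N from 100 to 400 and f and g each from 25% to 100%, n runs from 100 × 0.25 × 0.25 ≈ 6 to 400 × 1 × 1 = 400.
- N = 200, f = g = 1: n = 200. An alteration seen in 20/200 (10%) has an exact 95% interval of 6.2% to 15.0%.
- N = 200, f = g = 0.5: n = 200 × 0.5 × 0.5 = 50. The same 10% (5/50) has an interval of 3.3% to 21.8%.
- N = 200, f = 0.5, g = 0.25: n = 25. The chance of seeing a 5% alteration at least once is 1 − 0.95^25 ≈ 72%, against over 99% at n = 200.

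Precision can therefore vary widely, but it depends on N, f and g as they turn out. Section 10.5 sets none of them, and a corrected sentence would leave n unchanged.

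**The case for a change.** The best case for a change is that the sentence is wrong on its face and cheap to mend. The protocol has wording for an open offer (Section 4.1) and for the enrolled group (the Synopsis); Section 10.5 uses neither and says that all will be included. An exploratory label removes the need for a power calculation, not for a true account of who was studied. A reader of the progression results will want to know how many US subjects were lost at consent, at tissue collection, at progression and at re-biopsy.

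The first part stands: Section 10.5 is loosely worded and nothing in the protocol makes it literally correct. The need for clear counts in the report stands too, as ordinary good practice. What does not stand is the step from there to a change in the plan. No section makes Section 10.5 the base for reporting, and nothing prevents a participant-flow table. Under Sections 7.1.2 and 7.1.3.2 the requisition forms record consent and the reason for discontinuation, so these can be counted. Such a table would need care in any case. Companion consent is sought at screening, so some who consent may never reach the parent Full Analysis Set, and a chain running from that set to consented patients would not be nested unless restricted to its members.

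A comparison of participants with other US subjects could be informative, but it depends on what the parent trial's consent permits and is a matter of preference.

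**Conclusion.** No change to the plan follows. Section 10.5 overstates coverage, but its working sense is that there is no target and no cap: the study is open to every US subject of the parent trial, and whoever consents and provides tissue enters. Who enters and who is analysed are fixed elsewhere and consistently. The effect of the slip on any estimate, denominator or error rate is nil. The archival-timing difference between the two tables is a minor clerical matter of shipping dates with no shown effect on the analysed set.

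This rests on two assumptions: that the separate analysis plan takes each objective's denominator at the time point the objective needs, as Sections 3, 4.1 and 10 already imply, and that the report gives the numbers evaluable at baseline and at progression. If a report instead described its findings as covering all US subjects on the strength of Section 10.5, that would be an error in the report.
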